1. PURPOSE OF THE STUDY

a. Brief Summary

The purpose of this study is to compare effectiveness of duloxetine and desipramine in (1) decreasing pain, (2) improving function, (3) improving depression and (4) decreasing pain interference in patients with chronic pain. We will also compare compliance of patients with these two medications. We will apply a novel point of care randomization method which allows integration of randomized comparative effectiveness research with patient care.

b. Objectives

The importance of the proposed research has two aspects: 1) it establishes how pragmatic clinical trials can be integrated with patient care. This will lead to numerous more trials in future that can generate more evidence and direction for medical practice in perioperative and pain medicine; 2) it will determine if either a tricyclic antidepressant or a serotonin norepinephrine reuptake inhibitor is superior in treating patients with chronic pain. The subgroup analysis proposed will provide information about characteristics of patients who respond to these medications differently.

c. Rationale for Research in Humans

The study is comparing effectiveness of duloxetine and desipramine in patients with chronic pain. Administration of these medications to human subjects is necessary for the purpose of the study.

2. STUDY PROCEDURES

a. Procedures

Study Design: We will conduct a prospective open label randomized trial comparing effectiveness of duloxetine and desipramine.

Randomization (research): After obtaining research informed consent, the participants are going to be randomized by the treating pain provider using point of care randomization during the clinic visit. Point of care randomization will be done through Collaborative

Health Outcomes Information Registry (CHOIR) using computer generated random numbers.

Intervention: (standard of care) The participants are going to receive either duloxetine or desipramine. Duloxetine will be started at 20 mg per day. It will be increased to 40 mg per day at the beginning of week two, and then to 60 mg per day at the beginning of week three. Desipramine will be started at 25 mg per day. It will be increased to 50 mg per day at the beginning of week two, and then to 75 mg per day at the beginning of week three. These treatments will be continued for at least 6 months provided that the patients can tolerate the side effects and are willing to continue the treatment. Further titration of doses based on participants' tolerance and response is allowed based on clinical decision of the treating pain provider. Concomitant use of other analgesics or pain medications as well as pain interventions are also allowed.

Data collection: (standard of care and research) The participants are going to receive monthly electronic surveys which are already part of their routine clinical care. These surveys are going to be abbreviated to include average and worst Numerical Rating Scale (NRS) of pain; National Institute of Health (NIH) Patient Reported Outcomes Measurement Information System (PROMIS) measures for function, depression and pain interference; and questions about medication compliance, dose and adverse events. Data about use of other analgesics and medications, and pain interventions will also be recorded at these intervals from participants' electronic health records. If the participants do not complete the surveys within five days of receipt of the survey link, they will be contacted to be reminded of the survey. We will also record participants' baseline characteristics including age, sex, main pain diagnosis, other pain diagnoses, psychological comorbidities, medical comorbidities, medication use, and education.

b. Procedure Risks

The medications studied are both commonly used medications for patients with chronic pain. There is no additional risk with participation in the study.

c. Use of Deception in the Study

Deception will not be used.

d. Use of Audio and Video Recordings

Audio or video recording will not occur.

e. Alternative Procedures or Courses of Treatment

No alternative treatment is withheld from the patients.

f. Will it be possible to continue the more (most) appropriate therapy for the participant(s) after the conclusion of the study?

Participant will continue to receive their usual care from Stanford Pain Management Center after completion of the study. If one medication is proven to be superior, then the participants' physicians will be notified.

g. Study Endpoint(s)

We will not have any interim analysis; thus, we will be able to assess the superiority of one treatment at conclusion of the study.

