The study will terminate at the completion of follow-up for last patient enrolled. Study medication will be stopped if the participant decides to discontinue the medication. Since the medications used are part of standard clinical care that the patients receive in our clinic, the participants can continue the medication after the completion of the study if they would like to.

e. Data Safety Monitoring Plan (DSMC)

i. Data and/or events subject to review

The treatments in the study are not different from routine clinical practice; therefore, adverse events will be monitored as a part of participants' clinical care by their clinic providers. Protocol Director (PD) will monitor for protocol deviations.

ii. Person(s) responsible for Data and Safety Monitoring

Data and safety will be monitored by investigators and PD.

iii. Frequency of DSMB meetings

N/A

iv. Specific triggers or stopping rules

N/A

v. Will the Protocol Director be the only monitoring entity? (Y/N)

Yes

f. Risks to Special Populations

N/A

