Comparing Effectiveness of Duloxetine and Desipramine in Patients With Chronic Pain: A Pragmatic Trial Using Point of Care Randomization

Statistical Analysis Plan

NCT03548454

Revised March 28, 2025

Statistical Analysis. The initial sample size calculation determined that 107 participants per group would provide 90% power to detect a one-unit between-group difference in the NRS pain score ($SD=2.25$) at $\alpha=0.05$. However, the study was prematurely stopped due to most referred patients having prior experience with duloxetine or, less frequently, desipramine. As a result, we enrolled 38 patients in the desipramine group and 48 in the duloxetine group. With this sample size, we could detect a difference of 1.37–1.58 in NRS pain reduction with 80–90% power.

Participants were eligible if they completed at least one survey before being assigned a study medication and at least one follow-up survey. The baseline assessment was defined as the most recent survey before treatment assignment. Participants without follow-up surveys or those lost to follow-up were excluded. The primary analysis followed modified intention-to-treat (ITT) principles. However, within the first day of treatment assignment, five individuals switched from desipramine to duloxetine. To account for these switches, a per-protocol (PP) analysis was conducted, categorizing individuals based on the medication they took. For consistency, survey data (research and clinical surveys) were evaluated up to 52 weeks post-baseline when available.

Baseline demographic and clinical characteristics were summarized using three comparative analyses. First, a “per-protocol” approach was applied to compare demographic and clinical characteristics between the desipramine and duloxetine groups. Second, differences were assessed between participants who completed the full course of medication and those who discontinued early. Third, participants who achieved a clinically meaningful ($\geq 30\%$) pain reduction were compared to those who did not. Categorical variables were analyzed using Pearson’s Chi-square or Fisher’s Exact tests, while continuous variables were assessed using t-tests or Mann-Whitney U tests depending on normality.

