Longitudinal changes in pain intensity, physical function, and psychological function were analyzed using linear mixed-effects models (LMMs). Dependent variables included pain intensity (average and worst), PROMIS Pain Interference, PROMIS Anxiety, PROMIS Depression, and PROMIS Physical Function (Upper Extremity, Mobility, and Composite) scores. The primary independent variables were medication group (desipramine vs. duloxetine) and its interaction with time (weeks since baseline) to assess differential treatment effects. Baseline pain intensity was included as a covariate. A random intercept for each participant accounted for within-subject correlations. Various model structures were evaluated using Akaike Information Criterion and Bayesian Information Criterion, with final models selected based on model fit and diagnostic assessments. Model fit was evaluated using residual plots, Q-Q plots, histograms, and Variance Inflation Factor analyses. Bonferroni correction was applied to account for multiple comparisons. LOESS (Locally Estimated Scatterplot Smoothing) predicted values with 95% confidence intervals were plotted to visualize longitudinal trends stratified by medication group.

Kaplan-Meier survival analysis was used to evaluate medication adherence over time, conducted separately for both the intention-to-treat and per-protocol analyses. Time to discontinuation was calculated as the number of days between treatment initiation and discontinuation. Participants who completed the full course of medication were censored at the maximum observed follow-up duration. Kaplan-Meier survival curves were generated for each medication group, and the log-rank test was used to compare groups with 95% confidence intervals. A Kaplan-Meier survival analysis was also conducted to compare the time to achieving a $\geq 30\%$ reduction in average pain intensity from baseline between medication groups. A binary indicator variable was created to determine whether a participant met the pain reduction threshold at any follow-up point, with time-to-event defined as the earliest occurrence of this reduction. Participants who did not achieve the threshold were censored at 52 weeks. Kaplan-Meier survival curves were plotted separately for desipramine and duloxetine, with the log-rank test used for group comparisons.

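### The documents name no source for study-drug stop dates except the patient survey, so patients who stop both drug and surveys may drop out of the adherence comparison

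*Protocol*

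**What the plan says.** Protocol 1.a (Brief Summary) lists compliance as a comparison, after the four numbered effectiveness aims: "We will also compare compliance of patients with these two medications".

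Protocol 2.a (Procedures, Data collection) sets up two data streams:
- The monthly electronic survey, which the patient completes, carries "questions about medication compliance, dose and adverse events".
- The health record supplies the rest: "Data about use of other analgesics and medications, and pain interventions will also be recorded at these intervals". The study drug is not named here.

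Under the same paragraph, a patient whose survey is still unanswered after five days gets a reminder contact. No question about the drug is described at that contact. Protocol 7.d (Study Conclusion) adds: "Study medication will be stopped if the participant decides to discontinue the medication". It does not say that the date is recorded.

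The SAP defines the adherence endpoint in days: "Time to discontinuation was calculated as the number of days between treatment initiation and discontinuation". It does not say where the stop date comes from. Its adherence censoring rule covers only patients who finished the course, who are censored at the longest follow-up observed. On everyone else who goes quiet, the applicable text is: "Participants without follow-up surveys or those lost to follow-up were excluded". The SAP also reports that five patients moved from desipramine to duloxetine within a day of assignment, again without a source.

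**The concern.** If stop dates come from the survey, a stop is seen only when the patient answers at least once afterwards. A patient who gives up the drug and the surveys together has no recorded stop. The written rules then either remove that patient or leave the censoring time undefined. The missing events are the ones the Kaplan-Meier curve is meant to count.

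Three analyses depend on the same status: the time-to-discontinuation curves with their log-rank test, the baseline comparison of completers with early discontinuers, and the chi-square test relating adherence to a 30% pain reduction. The trial is open label and the two drugs may be stopped for different reasons, so silence after stopping need not be equal in the two arms.

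**Working it through.** **Plan's own figures.** There is no sample size, event count or power for the compliance comparison. The SAP's 107 per group (one NRS unit, SD 2.25, alpha 0.05 taken as two-sided, 90% power) reproduces, and so does its detectable difference of 1.37 to 1.58 with 38 and 48 patients. Both concern pain and do not bear on this point.

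**Set-up.** All inputs below are assumptions, because the documents give no stopping or non-response rates. Let *s* be the true share who stop, *q* the share of stoppers who fall silent with no stop date, and *r* the share of continuers who fall silent.

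- Silent patients excluded: observed = s(1−q) / [s(1−q) + (1−s)(1−r)]
- Silent stoppers kept as non-stoppers: observed = s(1−q)

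**One arm, s = 0.40.**

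| q | r | Excluded | Kept as non-stoppers |
|---|---|---|---|
| 0.10 | 0 | 0.36/0.96 = 37.5% | 36% |
| 0.25 | 0 | 0.30/0.90 = 33.3% | 30% |
| 0.50 | 0 | 0.20/0.80 = 25.0% | 20% |
| 0.25 | 0.25 | 0.30/0.75 = 40.0% | 30% |
| 0.25 | 0.40 | 0.30/0.66 = 45.5% | 30% |

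Under exclusion, the sign of the error depends on whether stoppers or continuers fall silent more often. Equal silence leaves the proportion unbiased only under exclusion. If silent stoppers are instead kept as non-stoppers, stopping is understated whatever *r* is.

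**Two arms, true 50% v 35% (15 points), silent patients excluded, r = 0.**

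| q, first arm | q, second arm | Observed | Difference |
|---|---|---|---|
| 0.25 | 0.25 | 0.375/0.875 = 42.9% v 0.2625/0.9125 = 28.8% | 14.1 points |
| 0.50 | 0.25 | 0.25/0.75 = 33.3% v 28.8% | 4.6 points |
| 0.25 | 0.50 | 42.9% v 0.175/0.825 = 21.2% | 21.6 points |

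The difference can shrink or grow. By the same formula, a true 35% in both arms with q of 0.50 and 0.25 shows as 21.2% v 28.8%, a false gap of 7.6 points.

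**Log-rank test at 38 v 48.** A simulation used exponential stopping times, six monthly surveys with 85% answered, and r = 0. With q of 60% v 20%, a true 35% in each arm appears as about 16% v 30% if silent stoppers are censored at their last survey. The false-positive rate is then roughly a quarter. If they are excluded instead, it is about 20%. If continuers fall silent as often as stoppers in each arm and lost patients are excluded, the arms again show about 35% v 35%. The assumption that continuers never go silent therefore drives the result, and a threefold difference between arms in silence is a strong assumption.

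**The case against.** A reader might infer that stop dates came solely from surveys and that stopping is therefore understated. The documents support neither step.

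- **Source.** That the survey is the sole source is an inference from silence. In the health-record sentence, the word other may attach only to analgesics. The first-day switches are dated more finely than a monthly survey would be likely to allow, and an endpoint in days fits a clinic or prescribing record just as well. The clinic writes the prescriptions and keeps patients under regular follow-up (Protocol 6.g and 7.c). The SAP also draws on clinical surveys up to 52 weeks. This stands: another source was probably used at least in part. But it is not described, and nothing shows that it covered every patient or later stops.
- **Direction.** Under the SAP's exclusion, understatement needs stoppers to fall silent more often than continuers. That is plausible but not shown. This stands in full: equal silence gives no bias under exclusion, and more silence among continuers gives overstatement.
- **Reach.** Some patients will report stopping before they go quiet, and non-responders are reminded. The gap is limited to those who answer nothing after stopping.
- **Weight.** Compliance lies outside the four numbered aims, and self-reported adherence is common in pragmatic open-label trials. That bears on priority. It does not supply a source for the stop date or a rule for patients who fall silent.

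**Conclusion.** The concern holds in limited form. The survey is the only source that the documents name for study-drug use. The SAP does not say how stop dates were obtained, and beyond excluding patients it gives no rule for non-responders in the adherence analysis. A patient who stops the drug and then stops answering may have no stop date and leave a stated comparison.

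Whether this biases the result depends on facts the documents do not give. If stoppers fall silent more often than continuers, stopping is understated. If silence also differs by arm, the between-drug comparison is biased in an unknown direction. If stoppers and continuers fall silent equally often, exclusion leaves the proportion unbiased. The figures above are illustrations under assumed silence rates, and most assume that no continuer goes silent; they are not estimates for this trial. The point should be addressed because the remedy is cheap and still feasible.

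**What to change.** **Data (Protocol 2.a).** Extend the health-record extraction to the study drug: first prescription, renewals, switch and stop date. Do this in the same way in both arms, for every randomised patient, whether or not surveys were answered. The SAP reports the trial as stopped early with 38 + 48 = 86 patients enrolled, so this is a retrospective extraction on a small number of charts.

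**SAP.**
- State the source of each stop date, record and survey, with the order of precedence.
- Keep non-responders in the adherence analysis using the record data.
- Add a sensitivity analysis that counts lost patients as discontinued at last contact.

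Where only surveys bound a stop, treating the date as lying between two answers is optional.

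**Cost.** A small amount of extra chart work and a few SAP sentences. Records show prescribing rather than intake, so survey answers should stay as a second source.

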3. BACKGROUND

a. Past Experimental and/or Clinical Findings

Chronic pain is a major healthcare problem affecting more than 100 million Americans. Chronic pain is a disease that can significantly compromise patients' quality of life and cause disability. It bears annual cost of around 635 billion Dollars on United States Healthcare System. The number of treatment modalities available for this condition is disproportionately low; moreover, the quality of data available for these modalities is not optimal either.(1) Pain medicine literature like other specialties faces problems with reproducibility and generalizability. In an attempt to test reproducibility of present literature, investigators could reproduce the results of only six (11%) out of 53 hematology-oncology trials. Interestingly, all these manuscripts had been published in reputable peer-reviewed journals with impact factors of above five.(2) We do not expect perioperative and pain medicine literature to be remarkably different.

The other problem with current literature is generalizability of the data. Large clinical trials usually have stringent inclusion and exclusion criteria. By restricting enrollment of patients with more serious comorbidities and psychological conditions, the observed differences can be attributed to interventions studied. By decreasing variability, statistical power to detect a treatment effect can be increased with the same number of patients. The disadvantage of this approach is that the results cannot easily be generalized to a large population of patients with more serious comorbidities and psychological conditions. This cohort of the patient is usually more difficult to treat.(3,4) Our current literature lacks high quality data to guide clinicians providing care to these patients. A simple example is implant to trial ration in patients undergoing trial of spinal cord stimulation. Most large clinical trials show that around 90% of patients have a successful trial of spinal cord stimulation and proceed with implantation.(5) However, case series published by large academic centers report that around 70% of the patients undergoing trial of spinal cord stimulation proceed to receiving an implanted device. (6,7) Comparative effectiveness research integrated with patient care can be one of the solutions to the current problem. These trials have a less stringent inclusion and exclusion criteria targeting patients who routinely receive clinical care. Therefore, the patients enrolled in these studies will better represent patients with chronic pain. Integration of research into patient care will allow enrollment of larger number of patients. This will enable the researchers to analyze known and unknown effects of treatments in the whole sample as well as in specific subgroups.^{3,4} Outcomes Research Consortium has already shown the benefits of this approach in perioperative medicine.(8) Comparative effectiveness trials focus more on effectiveness rather than efficacy. A specific treatment might be efficacious but not effective, especially in long term administration. In addition to efficacy, there are other factors than can affect effectiveness of a treatment including compliance, accessibility, ease of administration, etc. In chronic conditions, it is essential

to study long term effectiveness of a treatment modality in order to achieve meaningful sustainable improvement for patients.

We will leverage the advantages of a comparative effectiveness trial to answer an important question in pain medicine. Antidepressants are widely used to treat patients with chronic pain. Initial choice of antidepressant is usually based on clinical judgement of the clinician considering potential benefits versus risks of individual medications. Two most important classes of antidepressants used in patients with chronic pain are tricyclic antidepressants (TCAs) and serotonin norepinephrine reuptake inhibitors (SNRIs). Duloxetine is an SNRI that is approved by United States Food and Drug Administration for treatment of fibromyalgia, painful diabetic neuropathy and chronic musculoskeletal pain. Two previous small size trials compared the efficacy of duloxetine with TCAs after a short course of treatment (4-6 weeks). The investigators could not find a difference between duloxetine and amitriptyline.(9,10) Moreover, meta-analysis of studies that compared these two groups of medications with placebo could not find any difference between these medications. However, none of the initial trials included in the meta-analysis compared these TCAs and SNRIs directly.(11) One retrospective study showed decreased healthcare utilization in patients prescribed duloxetine compared to patients taking amitriptyline, pregabalin or gabapentin.(12,13)

While most TCAs share the side effect of drowsiness, desipramine can be a better comparison for duloxetine. Like duloxetine, desipramine does usually not cause sleepiness or drowsiness. To the best of our knowledge, there has not been any clinical trials comparing long-term efficacy or effectiveness of duloxetine and desipramine.

b. Findings from Past Animal Experiments

Not applicable

4. DRUGS, BIOLOGICS, REAGENTS, OR CHEMICALS USED IN THE STUDY

a. Investigational Drugs, Biologics, Reagents, or Chemicals

N/A

b. Commercial Drugs, Biologics, Reagents, or Chemicals

Commercial Product 1	
Name:	Duloxetine
Dosage:	20-120 mg per day
Administration Route	Oral, Capsule
New and different use? (Y/N)	No
Commercial Product 2	
Name:	Desipramine
Dosage:	25-150 mg per day
Administration Route	Oral, Tablet
New and different use? (Y/N)	Yes

